3.2 Objectives and Outcomes

| OBJECTIVES | ENDPOINTS (OUTCOME MEASURES) |
|------------|--|
| Primary | 
Evaluation of the acute safety of the EmitBio™ RD19 device. 
Frequency, grade and attribution of each incident local and systemic AE during the 14 day study period.Frequency and attribution of any incident SAEs during the 14 day study period. |
| Secondary | 
Evaluation of the acceptability of the EmitBio™ RD19 device. 
Ease of use, clarity of user instructions, & compliance with per protocol schedule and, if out of compliance, reason(s) for noncompliance. |

3.3 Scientific Rationale for Study Design

The EmitBio™ RD19 device is designed to place a protective countermeasure in the hands of at population-risk individuals in order to reduce the incidence of SARS-CoV-2 and COVID-19. At population-risk individuals are those living where community-transmission of SARS-CoV-2 is likely to occur and where community transmission is actively occurring. Through the identified mechanisms of virus killing and inhibition of virus replication, the RD19 device is expected to reduce SARS-CoV-2 viral load which in combination with other lifestyle measures, may help reduce the incidence of SARS-CoV-2 infection. This type of active protection is urgently needed for high-risk individuals (e.g. individuals exposed to a known infected person and healthcare workers and eldercare facility staff exposed to SARS-CoV-2 infected / COVID-19 patients and residents, respectively). The RD19 device has been engineered with the intent to help curb community transmission of SARS-CoV-2, thereby reducing the incidence of COVID-19. The CDC estimates that 40% of secondary coronavirus transmission occurs before people feel ill, highlighting the need for a broadly distributed protective countermeasure.

The RD19 optical illumination device is inserted into the mouth to shine light on the proximal repository for respiratory tract pathogens in the pharynx. The RD19 device uses a precise color of visible blue light (absent of UV light) to stimulate host defense and eliminate invading pathogens. This color of blue light has been found to both stimulate the instantaneous release of the body's reserves of nitric oxide and to increase endogenous production of nitric oxide in barrier epithelial cells. This naturally produced nitric oxide is substantially elevated over background levels and promotes innate immune responses capable of disrupting SARS-CoV-2 infection and inhibit viral replication of human coronaviruses. In addition to its direct antiviral activity, nitric oxide is an important pro-inflammatory cell signal to elicit induction and recruitment of other innate immune effectors, including NK cells, neutrophils, and macrophages.

3.4 Justification for Dose

In repeated experiments, including experiments conducted by third party external laboratories, it has been determined that the light emitted by the EmitBio™ RD19 device provides for potent antiviral activity against SARS-CoV-2. Reductions in viral infectivity of $\geq 99\%$ have been observed after a single illumination at an energy level of 9 Joules/cm². Separately, the yield of replicating SARS-CoV-2 virus in infected cells is inhibited by $\geq 99.9\%$ in the range of 9 – 15 J/cm². Dosing twice a day (total of 18 J/cm²) also allows endogenous nitric oxide levels to be elevated to an extent and for a time period expected to result in high level antiviral effects.

4. STUDY POPULATION

Twenty-five (25) males and non-pregnant females, 18 to 45 years of age inclusive, who are in good health and meet all eligibility criteria will be enrolled. The target population should reflect the community at large. The estimated time from initiation of enrollment to completion of the day 1 visit for the last subject enrolled is one week.

Subject Inclusion and Exclusion Criteria must be confirmed by a study clinician, licensed to make medical diagnoses and signatory to The Statement of Compliance as the site PI. Exemptions will be only be granted on Subject Inclusion or Exclusion in rare instances and based on the approval of the Sponsor's Chief Medical Officer.

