4.1 Full Inclusion Criteria

A subject must meet all of the following criteria to be eligible to participate in this study:

1. Provides written informed consent prior to initiation of any study procedures.
2. Agrees to comply with planned study procedures and be available for all study visits.
3. Agrees to the collection of venous blood per protocol.
4. Male or non-pregnant female, 18 to 45 years of age, inclusive, at time of enrollment.
5. Body Mass Index 18-35 kg/m², inclusive, at screening.
6. Woman of childbearing potential must have a negative urine pregnancy test within 7 days prior to study initiation.
7. Oral temperature is less than 100.0°F (37.8°C).
8. Pulse no greater than 90 beats per minute.
9. Systolic BP is 85 to 150 mmHg and Diastolic BP ≤ 90 mmHg, inclusive.
10. Clinical screening laboratory evaluations are within acceptable normal reference ranges at the clinical laboratory being used.

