4.2 Full Exclusion Criteria

A subject who meets any of the following criteria will be excluded from participation in this study:

1. Positive urine pregnancy test at screening.
2. Has any medical disease or condition that, in the opinion of the site PI or appropriate sub-investigator, precludes study participation.¹
3. Plans to travel away from the study site area during the term of study to a location or in a manner that may interfere with full completion of the study per protocol.
4. Presence of self-reported or medically documented significant medical or psychiatric condition(s).²
5. Has an acute illness³, as determined by the site PI or appropriate sub-investigator, with or without fever [oral temperature $>37.8^{\circ}\text{C}$ (100.0°F)] within 72 hours of study day 1.
6. Reports a recent positive test result for hepatitis B surface antigen, hepatitis C virus antibody, or HIV-1 antibodies at screening.
7. Currently enrolled in or plans to participate in another clinical trial with an interventional investigational agent that will be received during the study period.⁵
8. Has a history of hypersensitivity or severe allergic reaction (e.g., anaphylaxis, generalized urticaria, angioedema, other significant reaction) to nitrates, nitrites or sun exposure.
9. Active use of any medications that may be associated oral pharyngeal or mucosal irritation.
10. Has any blood dyscrasias or significant disorder of coagulation.
11. Has a history of alcohol abuse or other recreational drug (excluding cannabis) use within 1 month of Study Day 1.
12. Has any oral abnormality that would interfere with device use, or intra-oral metal body piercings that cannot be removed for the duration of the study. Metal orthodontia is permitted as braces will be covered by the device mouthpiece.
13. Receipt of any other SARS-CoV-2 or COVID19 experimental coronavirus investigational product within 30 days of screening.

¹*Including medical diseases or conditions that would place the subject at an unacceptable risk of injury, render the subject unable to meet the requirements of the protocol or may interfere with the evaluation of responses or the subject's successful completion of this trial.*

²*Significant medical or psychiatric conditions include but are not limited to: respiratory disease (e.g., chronic obstructive pulmonary disease [COPD], asthma) requiring current daily medication.*

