7. STATISTICAL CONSIDERATIONS

7.1 Statistical Hypotheses

This is a phase I, open-label, safety study and is not designed to test any statistical hypotheses. Rather, this is a descriptive study intended to obtain preliminary estimates in healthy adults of the safety, including reactogenicity, of the EmitBio™ RD19 Device.

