7.2 Sample Size Determination

SAMPLE SIZE CONSIDERATION - OPEN LABEL

This study is designed as an open-label study, without a placebo arm. Given the small sample size, the use of a placebo group is unlikely to improve understanding of AEs. Additionally, having the study unblinded will facilitate the need for rapid review and dissemination of study data for public health reasons.

Rare AEs are not demonstrable in a clinical study of this size; however, the probabilities of observing one or more AEs given various true event rates are presented in the table below. With the assumption that all enrolled subjects will likely complete the trial and safety visits in this relatively short duration study, the following statistical considerations apply. With 25 subjects, the chance of observing at least one AE of probability 20% or more is approximately 97%. Therefore, if no AEs of a given type occur in the study, we can be 97% confident that they will occur in fewer than 20% of people once RD19 is implemented. Also with 25 subjects, the chance of observing at least one AE of probability 5% or more is 90%. Therefore, if no AEs of a given type occur in the study, we can be 90% confident that such adverse event will occur in fewer than 5% of people once RD19 is implemented.

| N | “True” Event Rate | Probability of Observation (%) |
|---|-------------------|--------------------------------|
| 2 | 0.1% | 2.5 |
| | 0.5% | 12.0 |
| | 1.0% | 23.4 |
| | 2.0% | 43.4 |
| | 3.0% | 61.3 |
| | 4.0% | 74.8 |
| | 5.0% | 90.3 |
| | 10.0% | 92.4 |
| | 15.0% | 94.3 |
| | 20.0% | 97.5 |

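### Section 7.2 states its zero-event bounds for RD19 users in general, but the design supports them only for screened-healthy adults aged 18 to 45 over 14 days, and the percentages need correcting in the same edit

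*Combined protocol and SAP*

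**What the plan says.** **Who is enrolled.** Section 4 enrols "Twenty-five (25) males and non-pregnant females, 18 to 45 years of age inclusive, who are in good health and meet all eligibility criteria". The next sentence reads "The target population should reflect the community at large". Section 4.1 adds limits on BMI, pulse, blood pressure and temperature, and the criterion "Clinical screening laboratory evaluations are within acceptable normal reference ranges at the clinical laboratory being used". Section 4.2 and its footnotes exclude, among others, people with significant cardiovascular disease, airway disease needing daily medication, autoimmune disease, immunodeficiency, blood dyscrasias, or hypersensitivity to nitrates, nitrites or sun. They also exclude "Active use of any medications that may be associated oral pharyngeal or mucosal irritation".

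**For how long.** The endpoints in Section 3.2 and the reporting period in Section 6.2.1 run from first device use on Day 1 to Day 14.

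**What is aimed at.** Section 7.1 says that "this is a descriptive study intended to obtain preliminary estimates in healthy adults of the safety".

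**What is concluded.** Section 7.2 turns an absence of events into two confidence statements. At 97%, events of that type are such that "they will occur in fewer than 20% of people once RD19 is implemented". At 90%, the same is said of 5%. Both are worded for people in general after implementation, with no limit on age, health or length of use.

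**The concern.** A zero-event binomial bound describes the population and exposure period that were sampled. Section 7.2 attaches it to something wider. Section 7.1 has the narrower and correct target, so the two sections disagree on what the trial can conclude.

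The gap matters for this device. Several of the exclusions (light and nitrate hypersensitivity, drugs that irritate the mucosa, blood disorders) concern people in whom a light device said to act through nitric oxide might plausibly behave differently. The proposed claim in Section 1.1.1 states no age, health or duration limit, and Section 3.3 describes a broadly distributed countermeasure.

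Section 5.1.1 says the safety data will be useful for determining the regulatory pathway, and Section 7.2 itself anticipates rapid dissemination. A conclusion already worded for future users could pass unchanged into the study report.

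**Working it through.** **1. Scope, side by side**

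| | Observed | Stated in 7.2 |
|---|---|---|
| Population | 25 healthy adults, 18 to 45, normal screening laboratory values (4, 4.1, 4.2) | People, without limit |
| Period | Day 1 to Day 14 (3.2, 6.2.1) | After implementation, without limit |

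**2. The plan's own figures**

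Inputs: n = 25, with all participants assumed to complete (7.2). The chance of at least one event is 1 − (1 − p)^25.

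| True rate p | Plan's table (%) | Computed (%) |
|---|---|---|
| 0.1% | 2.5 | 2.5 |
| 0.5% | 12.0 | 11.8 |
| 1% | 23.4 | 22.2 |
| 2% | 43.4 | 39.7 |
| 3% | 61.3 | 53.3 |
| 4% | 74.8 | 64.0 |
| 5% | 90.3 | 72.3 |
| 10% | 92.4 | 92.8 |
| 15% | 94.3 | 98.3 |
| 20% | 97.5 | 99.6 |

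Four rows (0.1%, 0.5%, 1% and 10%) agree within 2 points; six do not. No single n fits: the 5% row implies about 45 subjects and the 20% row about 17. For the two sentences in the text:

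- 5%: 1 − 0.95^25 = 72.3%, against a stated 90%.
- 20%: 1 − 0.80^25 = 99.6%, against a stated 97%.

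**3. What 0 of 25 does bound, over 14 days, in the enrolled population**

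The one-sided upper limit at confidence C is 1 − (1 − C)^(1/25).

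- 90%: 1 − 0.10^(1/25) = 8.8%
- 95%: 1 − 0.05^(1/25) = 11.3%
- 97%: 1 − 0.03^(1/25) = 13.1%

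**4. Longer use**

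The documents give no hazard shape, so two assumptions mark out a range for the 97% limit.

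- All reactions occur within the first 14 days: the limit stays at about 13.1%, whatever the horizon.
- Constant daily hazard: 1 − (1 − 0.1309)^(30/14) = 26.0% at 30 days, and 1 − (1 − 0.1309)^(90/14) = 59.4% at 90 days. The 20% mark is passed at 14 × ln(0.80)/ln(0.8691), or about day 22.

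**5. Other populations**

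The data give no bound for excluded groups. As an illustration only, on assumed figures: if half of eventual users resemble the sample and the rest carry 2 to 3 times the risk, the 95% limit of 11.3% becomes 0.5 × 11.3 + 0.5 × 22.6 = 16.9%, up to 0.5 × 11.3 + 0.5 × 33.9 = 22.6%.

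**The case against.** **Healthy volunteers are a normal phase I choice.** This stands. The stated objective is acute safety, and the eligibility criteria are not at fault. Only the reach of the conclusion is.

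**The Section 4 sentence may mean demographic mix.** This also stands. It directly follows the description of eligible healthy adults, and Section 7.4.3 summarises age, sex, ethnicity and race. A reader might infer that Section 4 contradicts its own eligibility criteria, but the text is ambiguous and does not establish that.

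**The limits are already stated.** This holds only in part. Section 7.1 restricts the aim to healthy adults, and Section 7.2 concedes that rare events cannot be shown. The concession concerns event frequency. It does not limit population or duration, and the two confidence sentences carry neither limit.

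**Implementation is not defined, and Section 3.3 names people at high risk by exposure, not by age or illness.** This is correct. Older or chronically ill users are not named as intended users. They are not ruled out either, so the unqualified wording still exceeds what is observed.

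**The long-term figures depend on one assumed hazard.** This is also correct, which is why a range is given. A reader might infer that the plan claims long-term safety, or that the risk at 90 days really is near 59%. The documents support neither.

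A reader might also infer that these sentences are the plan's only inference, or that the regulatory pathway turns on them. Section 7.4.1 plans exact confidence intervals for solicited and unsolicited events, and Section 5.1.1 says only that the data will be useful.

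**Conclusion.** The point holds as one of scope. Section 7.2 states bounds for future users in general that come from 25 screened-healthy adults aged 18 to 45 followed for 14 days. Section 7.1 already has the right target.

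Restricting the scope alone is not enough. Within the enrolled population the 20% sentence becomes true and conservative (99.6% against 97%), but the 5% sentence stays false (72.3% against 90%). Both faults should be corrected together.

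The limits of 8.8%, 11.3% and 13.1% assume independent participants and that all 25 are observed for the full 14 days. Nothing beyond 14 days, and nothing in excluded groups, is bounded without further assumptions. This does not change the design or conduct of the trial, but it does change what the trial may conclude, so it should be amended.

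**What to change.** 1. In both sentences of Section 7.2, replace the closing reference to people after implementation with: *of healthy adults meeting the eligibility criteria, aged 18 to 45, using RD19 twice daily for up to 14 days*.
2. In the same edit, correct the percentages: with no events in 25, confidence is 72.3% that the rate is below 5% and 99.6% that it is below 20%. Equivalently, give the one-sided upper limits of 8.8% (90%), 11.3% (95%) and 13.1% (97%). Correct the table rows to match.
3. Use the same limit on population and duration in the study report's conclusion.
4. As a secondary change, clarify in Section 4 that the sentence on the community refers to demographic mix among eligible healthy adults.

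The cost is wording only: enrolment, visits and device use do not change. The stated conclusion becomes narrower, and the 5% statement loses most of its force. To keep 90% confidence at 5% with no events would take 45 subjects (1 − 0.95^45 = 90.1%). That is not proposed here.

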3. STUDY DESIGN

3.1 Overall Design

This first-in-man (FIM) phase I study will evaluate the acute safety, tolerability, and device acceptability for use among 25 healthy volunteers between the age of 18 and 45. Based on the results of numerous preclinical studies, a single dose (9 joules/cm²) and schedule (twice a day, separated by at least 4 hours, preferably 8 to 12 hours apart) will be evaluated.

Safety and tolerability (local reactogenicity) will be assessed actively at the following study days: screening (baseline set), 1, 7 and 14, and on non-clinic visit days by collection of these data by history during clinic visits via a memory aid (diary cards). Volunteers will be encouraged to promptly contact designated clinical trial staff or the one of the Sponsor's Emergency Response Team for AEs of a medically urgent nature.

A Comprehensive Metabolic Panel, as well as CBC with differential, urinalysis, and pregnancy testing will be performed at screening and at Day 14 or early termination (and potentially during unscheduled) clinic visits. Hematological safety assessments (evaluation of methemoglobinemia) will be performed at all visits.

Study volunteers will be asked to immediately contact the clinical coordinator and/or the PI in all instances where they experience an AE of greater than moderate intensity. Volunteers will be instructed to report to the clinical trial unit for an unscheduled visit or to seek the appropriate level of medical care based on the nature of their AE/SAE. In all such instances, all relevant information pertaining to these significant medical events will be captured on the appropriate e-CRFs.

Hematology safety laboratory evaluations will be performed at screening, as well during all scheduled clinic visits. Laboratory assessments may be part of the evaluation of medically attended AE evaluation and for all SAEs.

Upon ratification of the CTA, the site will begin pre-recruitment outreach efforts of potential volunteers within M3-WRA's database to ascertain "interest in general" in this study. Official recruitment which may include fliers, letters, telephone calls, etc. and specific recruitment of potential subjects who have previously participated in other clinical studies conducted at the site will occur only after formal IRB approval. Other forms and/or mechanisms of recruitment may also be used. The IRB will approve the recruitment process and all materials prior to use.

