7.3 Populations for Analyses

The full safety analyses population is by intention-to-treat (ITT) including all subjects who received at least a single use of RD19.

A modified per protocol population for analyses will include all study volunteers who complied with study procedures and remained on study, per protocol, until at least the day 7 clinic visit.

The per protocol population for analyses will include all study volunteers who complied with all protocol procedures and remained on the study until their day 14 visit.

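### Section 4 lets the sponsor exempt subjects from eligibility criteria that 4.1 and 4.2 make absolute, and nothing keeps an exempted subject out of the per-protocol sets

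*Combined protocol and SAP*

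**What the plan says.** Section 4 describes the 25 subjects as people "who are in good health and meet all eligibility criteria will be enrolled". Its next paragraph, after requiring a licensed study clinician to confirm the criteria, adds: "Exemptions will be only be granted on Subject Inclusion or Exclusion in rare instances" and "based on the approval of the Sponsor's Chief Medical Officer".

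The two lists that follow are absolute. Section 4.1 opens: "A subject must meet all of the following criteria to be eligible to participate in this study". Section 4.2 opens: "A subject who meets any of the following criteria will be excluded from participation in this study". Neither refers to exemptions.

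Section 7.3 defines the safety population as "including all subjects who received at least a single use of RD19". The per-protocol population is made up of volunteers "who complied with all protocol procedures and remained on the study until their day 14 visit". The modified per-protocol population uses the same idea with a day 7 cut-off. Eligibility is not a condition of any of the three.

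Section 1.1.4 makes the Chief Medical Officer the medical monitor and, together with the investigators, part of the team that attributes severe and serious adverse events.

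**The concern.** Section 3.1 sets the context: "This first-in-man (FIM) phase I study will evaluate the acute safety, tolerability, and device acceptability for use among 25 healthy volunteers". In such a study the eligibility list does two jobs. It protects subjects from a first exposure that the protocol considers unsuitable for them, and it defines the healthy adults whom section 7.1 says the estimates describe.

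An open waiver weakens both. A subject whom the protocol itself calls ineligible can use the device on a sponsor decision with no stated outside check. That subject can then pass unmarked into analyses labelled per-protocol, and a reader of the report could not tell that the described population had changed.

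**Working it through.** This is mainly a comparison of texts. The plan gives no figure for exemptions, so there is none to reproduce, and the detection probabilities in 7.2 are not an input.

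1. **Do the texts conflict?** Section 4 says that all enrolled subjects meet all criteria; 4.1 requires all; 4.2 excludes on any one. The exemption sentence allows enrolment when one of these fails. Both cannot hold for the same subject. Judgement written into a criterion (exclusion 2, or footnote 3 on nearly resolved illness) is different: it decides whether the criterion is met and does not waive it.

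2. **How far does the waiver reach?** The sentence covers inclusion and exclusion alike and lists nothing as non-waivable. Two requirements stand independently: consent before any study procedure (8.1.1) and a negative pregnancy test before device use (6.2, clinical laboratory evaluations). The rest is within reach, including exclusion 8 (hypersensitivity to nitrates, to nitrites or to sunlight) and exclusion 10 (blood dyscrasias and coagulation disorders).

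3. **Who would see an exemption?** The clause names only the Chief Medical Officer. Section 8.1 requires IRB approval of amendments, but a single waiver is not an amendment. Section 8.1.8 sends deviations to the IRB and defines them as non-compliance with the protocol. An enrolment that the protocol permits is arguably compliant, so whether it is reported is left open.

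4. **Where would the subject be analysed?** One device use puts the subject in the safety population, which is standard and right. If the subject also follows procedures and stays to day 7 or day 14, the wording of 7.3 admits that subject to the modified or full per-protocol set. Those sets feed the dichotomised solicited-event summary in 7.4.1 and the acceptability summaries in 7.4.2. Sections 7.4.1 to 7.4.3 contain no flag, listing or sensitivity analysis for exempted subjects.

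5. **Size.** Share of the sample = k/25 for k exemptions. The documents give no k; assuming 1 to 3 for illustration:
   - k = 1: 1/25 = 4%
   - k = 2: 2/25 = 8%
   - k = 3: 3/25 = 12%

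6. **Precision lost by leaving such subjects out of a per-protocol set.** With zero events, the exact two-sided 95% upper limit is 1 − 0.025^(1/n). If every other subject qualifies:
   - n = 25: 13.7%
   - n = 24: 14.2%
   - n = 23: 14.8%
   - n = 22: 15.4%

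   The exclusion therefore costs little precision.

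**The case against.** The clause has two stated brakes, rarity and a senior medical approval. It does not oblige the site to enrol anyone: a licensed clinician confirms the criteria (section 4) and is responsible for study-related medical decisions (6.2). It would equally cover a trivial failure, such as a pulse of 91 against a limit of 90. The sponsor classes the device as not significant risk. These points stand and limit the severity, but they neither remove the contradiction nor fill the gap in 7.3.

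Deletion also has a cost. The repeat measurement and re-screen in 6.1.1 help only with transient failures or measurement problems, or with a criterion that will be met on re-screening within 2 days. Inclusion 10 asks for laboratory values within reference ranges, and a stable, unimportant outlier would still exclude. As an illustration only, assume 10 to 30 independent analytes with 95% ranges: 1 − 0.95^10 = 40% and 1 − 0.95^30 = 79% of healthy people would have at least one value outside. Correlation between analytes, and the latitude in the wording of that criterion, would lower this. The extra screening is therefore real, but it cannot be quantified from the documents.

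Two stronger readings are tempting and do not hold:

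- **A shift in the upper limit.** A reader might infer that the harm is the move in the exact 95% upper limit from 13.7% (0/25) to 20.4% (1/25). One event in any subject, eligible or not, produces that shift, so it does not measure this defect.
- **Attribution.** A reader might infer that adverse events in exempted subjects cannot be attributed. Attribution is made event by event (6.2.9), alternate etiology is recorded (6.2.1), and many criteria, such as travel plans or BMI, have no evident bearing on it.

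**Conclusion.** The point holds as a contradiction within section 4 and between section 4 and sections 4.1 and 4.2, with a matching gap in 7.3 and 8.1.8. Followed as written, the plan can expose subjects it calls ineligible and count them as per-protocol, without clearly requiring that anyone outside the sponsor and the site be told.

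The size is 4% of the sample per exempted subject. The number is unknown and may be zero, so no effect on the estimates can be claimed. The per-protocol part of the conclusion rests on reading compliance with procedures in its plain sense, which does not include having met the entry criteria. Counting every treated subject in the safety population is not part of the criticism. The change is worth making before enrolment, but the point does not invalidate the design.

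**What to change.** Reconcile section 4 with 4.1 and 4.2. Deleting the exemption sentence is simplest, because the two lists then apply as written. If the sponsor keeps it, 4.1 and 4.2 must refer to it, and the protocol must say how an exemption is documented, reported to the IRB and listed.

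In 7.3, add that any subject found after first use not to meet the criteria:

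- stays in the safety population;
- is listed, and reported as a protocol deviation under 8.1.8;
- is left out of both the modified and the full per-protocol sets.

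The planned sample size does not change. The cost is one deleted sentence, one added statement and some additional screening to fill places. Section 4 allows about one week from the start of enrolment to the last subject's day 1 visit, so the site should plan for that screening in advance.
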